6.9.1. Causality Assessment

The Blinded Investigator will assign the causality assessment according to his/her clinical experience and the subject's description of the event. The Sponsor will be responsible for the final causality judgment. The causal relationship should be classified according to the following criteria (not all variables need to be present to be indicative of relationship to the treatment):

Definitely related:

- The temporal sequence of AE onset relative to study treatment is reasonable.
- The AE is more likely explained by study treatment than by another cause.
- The AE shows a pattern consistent with previous knowledge of study treatment.

Probably related:

- The temporal sequence of AE onset relative to study treatment is reasonable.
- The AE is more likely explained by the study treatment than by another cause.

Possibly related:

- The temporal sequence of AE onset relative to study treatment is reasonable.
- The AE could have been due to another equally likely cause.

Probably not related:

- There is another more likely cause of the AE.

Definitely not related:

- The temporal sequence of AE onset relative to study treatment is not reasonable.
- There is another obvious cause of the AE.

6.9.2. Severity Assessment

For all types of AEs, the Blinded Investigator will determine the severity classification based on his/her clinical experience and by using the following definitions of severity:

- **Mild:** Symptoms are barely noticeable or do not make the subject uncomfortable. The AE does not influence performance or functioning. Prescription drugs are not ordinarily needed for relief of symptom(s).
- **Moderate:** Symptoms are of sufficient severity to make the subject uncomfortable. Performance of daily activities is influenced. Treatment of symptom(s) with prescription drugs or therapies may be needed.
- **Severe:** Symptoms are of sufficient severity to cause the subject severe discomfort. Performance of daily activities is compromised. Treatment for symptom(s) with prescription drugs or therapies may be needed.

Version 1.1 31-May-2023 Confidential Page 16/58

The maximal severity for the AE will be recorded, even if the AE presented as being less severe at some point during the event.

Adverse Events of Special Interest (AESI) Reporting

6.9.3. Adverse Events of Special Interest (AESI) Reporting

AESI are important medical events that may be consistent with botulinum toxin effects, such as:

- Swallowing or breathing difficulties
- Asthenia
- Generalized muscle weakness
- Diplopia
- Dysphagia
- Dysphonia
- Dysarthria

6.9.4. Unexpected Adverse Drug Reaction (UADR) Reporting

A UADR is a treatment-related adverse reaction where the nature or severity is not consistent with the applicable product information in the Investigator's Brochure. An AE will be considered as a UADR if it is a treatment-related event not associated with the following Expected Adverse Drug Reactions:

- Headache
- Facial paresis (eyelid ptosis, brow ptosis)
- Blepharospasm
- Injection site pain
- Injection site hematoma
- Injection site reaction
- Eyelid edema
- Nausea

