#### 10.5.3 Unexpected Adverse Drug Reaction (UADR)

A UADR is an adverse reaction where the nature or severity of which is not consistent with the applicable product information in the source documents (e.g., Investigator's Brochure.).

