#### 12.5.1 Adverse Events (AEs)

AEs will be coded to system organ class (SOC) and preferred term (PT) using the Medical Dictionary for Regulatory Activities (MedDRA). The number and percentage (incidence) of subjects reporting an AE and the number of AEs will be summarized.

A treatment-emergent AE will be defined as AEs that started at or after the first injection.

The following AE incidence tables will be provided for treatment-emergent AEs:

- All AEs by SOC and PT
- Related AEs by SOC and PT
- All AEs by PT sorted by decreasing frequency among all subjects
- Related AEs by PT sorted by decreasing frequency among all subjects
- All SAEs by seriousness criterion
- Related SAEs by seriousness criterion

- All SAEs by SOC and PT
- Related SAEs by SOC and PT

Treatment-related AEs will be defined as possibly, probably, or definitely related. Two-sided Wilson 95% confidence intervals will be calculated for the overall incidence of AEs and SAEs.

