7.4.1. Adverse Events (AEs)

AEs will be coded to system organ class (SOC) and preferred term (PT) using the Medical Dictionary for Regulatory Activities (MedDRA). The number and percentage (incidence) of subjects reporting an AE and the number of AEs will be summarized. A treatment-emergent AE will be defined as AEs that started at or after the first injection.

The following AE incidence tables will be provided for treatment-emergent AEs:

- AE Profile Overview
- Treatment-Emergent AEs by SOC and PT
- Treatment-Related AEs by SOC and PT
- Treatment-Emergent SAEs by SOC and PT
- Treatment-Related SAEs by SOC and PT
- Unexpected Adverse Drug Reactions by SOC and PT
- Adverse Events of Special Interest by SOC and PT

Treatment-related AEs will be defined as possibly, probably, or definitely related. Two-sided Wilson 95% confidence intervals will be calculated for the overall incidence of AEs and SAEs.

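### AE severity is graded but reaches no planned AE table, and the UADR text can be read with or without its severity limb, so a non-serious worsening of known reactions at 40U would not be shown by grade

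*SAP*

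**What the plan says.** **Definition.** SAP 6.9.4 describes a UADR as a treatment-related reaction "where the nature or severity is not consistent with the applicable product information in the Investigator's Brochure". Protocol 10.5.3 has the same two limbs: "A UADR is an adverse reaction where the nature or severity of which is not consistent with the applicable product information".

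**Classification sentence.** Directly after the definition, SAP 6.9.4 says: "An AE will be considered as a UADR if it is a treatment-related event not associated with the following Expected Adverse Drug Reactions". Protocol 10.5.6.4 carries the same sentence and the same eight entries: headache; facial paresis (eyelid or brow ptosis); blepharospasm; injection site pain, hematoma and reaction; eyelid edema; and nausea. No entry has a severity grade.

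**Severity data.** SAP 6.9.2 and Protocol 10.5.5 grade AEs as mild, moderate or severe. On repeated grading, "The maximal severity for the AE will be recorded".

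**Tables.** SAP 7.4.1 states: "The following AE incidence tables will be provided for treatment-emergent AEs". Seven follow: an overview, treatment-emergent AEs, treatment-related AEs, the two SAE tables, "Unexpected Adverse Drug Reactions by SOC and PT", and AEs of special interest (AESI). Protocol 12.5.1 lists eight, sorted by SOC and PT, by PT frequency, or by seriousness (for example "All SAEs by seriousness criterion").

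**Setting.** Protocol 2 and SAP 1.4 make the safety of 40U part of the primary objective. Protocol 1.2 and SAP 1.2 give 20U as the approved total dose. SAP 7.6 plans 50 subjects per arm.

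**The concern.** Known reactions becoming more severe, rather than only more common, is a natural question when the dose is doubled. The plan collects the grade that would answer it and then leaves that grade out of every AE table it lists.

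The UADR table could have been a partial safeguard, because its definition reaches reactions of unexpected severity. But a site or programmer working from the list could treat a severe ptosis or headache as expected because of its type, while a colleague working from the definition could flag it. The same event could then enter or miss Table 14.4.1.6. It could also enter or miss the evaluation within 10 working days that Protocol 10.5.6.4 attaches to UADRs.

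**Working it through.** The plan states no figure on this point, so there is none to reproduce. The check compares the texts and goes through the tables, followed by one illustration.

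**1. Definition against classification sentence**

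| Event (treatment-related) | By the definition | By the list sentence |
|---|---|---|
| Type not on the list | UADR if the nature is not consistent with the Investigator's Brochure | UADR |
| Listed type, severity as described in the Brochure | Not a UADR | Not brought in |
| Listed type, severity beyond the Brochure | UADR | Not brought in |

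The third row is where the two sentences part. The Protocol repeats both, so it does not settle the matter.

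**2. Where does severity appear in the planned AE tables?**

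- SAP 7.4.1: 0 of 7 tables.
- Protocol 12.5.1: 0 of 8 tables.
- Shells: Table 14.4.1.1 has rows for treatment-emergent AEs, related AEs, SAEs, related SAEs, UADRs and AESIs. Tables 14.4.1.2 to 14.4.1.7 show participants and events by SOC and PT. None has a severity row or column.
- Table 14.4.5.1 (directed questionnaire) is yes/no.

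**3. What would still show a worsening?**

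- Worsening that meets a seriousness criterion: Tables 14.4.1.4 and 14.4.1.5. Protocol 10.5.5 itself notes that a severe AE and an SAE are different things.
- Higher frequency: Tables 14.4.1.2 and 14.4.1.3 and, for headache and drooping, Table 14.4.5.1.
- Indirectly: the physical exam and review-of-systems shift tables (14.4.2.3, 14.4.3.1), which grade clinical significance; AE discontinuations (14.1.2); and concomitant medications (14.2.4.1).

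What remains is a non-serious rise in severity of a listed reaction with unchanged frequency.

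**4. Illustration with assumed counts**

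Protocol 1.1 reports headache in 9.3% of 20U prabotulinumtoxinA subjects in the two US Phase III studies. With 50 per arm, 0.093 × 50 = 4.65, so take 5. Assume 5/50 in each prabotulinumtoxinA arm, all judged treatment-related, all mild at 20U and all severe at 40U. SAP 7.4.1 names the Wilson interval for overall incidence; it is applied here to single rows:

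(p + z²/2n ± z√[p(1−p)/n + z²/4n²]) / (1 + z²/n), with z = 1.96 and n = 50.

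- p = 5/50: (0.1384 ± 0.0916)/1.0768, or 4.3% to 21.4%.
- p = 0/50: upper limit 0.0768/1.0768, or 7.1%.

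| Output | 40U | 20U | Fisher two-sided p |
|---|---|---|---|
| Headache row as planned (14.4.1.2, 14.4.1.3) | 5/50, 10% (4.3 to 21.4) | 5/50, 10% (4.3 to 21.4) | 1.00 |
| Headache in UADR table, list applied literally | 0 | 0 | – |
| Severe headache, if tabulated by maximum severity | 5/50, 10% (4.3 to 21.4) | 0/50, 0% (0.0 to 7.1) | 0.056 |

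For 5 against 0, p = 2 × C(50,5)/C(100,5) = 2 × 2,118,760/75,287,520 = 0.056.

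**5. How many events might be graded at all?**

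Protocol 1.1 gives study-drug-related AE rates at 20U of 15.4%, 9.8% and 15.5% in the three Phase III studies, and 11.1% and 6.5% after the initial treatment in the two repeat-dose studies. Per 50 subjects the range is 0.065 × 50 = 3.25 to 0.155 × 50 = 7.75, or about 3 to 8. These are related AEs of any type and grade; the documents give no severe-event rate.

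**The case against.** A reader might infer that the UADR rule ignores severity and that a worsening of known reactions at 40U would be absent from the safety results. The documents do not support either statement.

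- **The wording is *if*, not *only if*.** Being off the list is sufficient for a UADR, but the sentence does not make it necessary. The severity limb stands immediately before it, and a careful coder could still flag a severe ptosis. This stands: the defect is ambiguity, not omission.
- **The benchmark is the Investigator's Brochure, which is not among the documents.** If it already describes severe headache or severe ptosis, such an event is not a UADR under either reading. This stands: no particular event can be shown to be misclassified.
- **The AESI list is introduced by example.** Ptosis is not named, but the list is not closed, so it cannot be said that the AESI table would miss it. This stands.
- **Other outputs carry information.** Serious or more frequent events are tabulated. The exam covers cranial nerves and muscle weakness, with findings graded by clinical significance. Protocol 11.3 withdraws subjects whose AE requires intervention in the injected region, and Table 14.1.2 counts AE discontinuations. The Medical Monitor reviews AEs regularly (Protocol 3.3). This stands in part. Clinical significance is not the AE grade. The concomitant medication table is not linked to AEs, and the definitions of moderate and severe say the same about prescription treatment. Monitoring is not a by-arm result.
- **Subject listings.** SAP 7.7 says data will be listed by subject, but no AE listing with severity is specified, and a listing is not a comparison of arms.
- **The counts are small and assumed.** Even the extreme 5-to-0 split gives p = 0.056. This stands, but SAP 7.4 plans descriptive safety summaries, so the case for a severity table does not depend on a test.

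**Conclusion.** The point holds in a limited form. Two sentences on UADR classification need to be reconciled, because a listed reaction of unexpected severity can be classified either way; all eight listed types are affected. Separately, maximum severity is recorded but appears in 0 of 7 SAP tables, 0 of 8 protocol tables and none of the AE shells. A non-serious increase in severity at 40U without higher frequency would not be visible by AE grade in any planned by-arm summary.

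The tabulation gap rests only on the table lists and shells. The UADR consequence depends also on what the Investigator's Brochure says and on how the sentence is applied. The illustration is an extreme case with invented severities; it shows that the planned rows cannot tell the two situations apart, not that such a shift is likely.

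This should be changed because safety at 40U is part of the primary objective. It does not make the planned safety analysis invalid.

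**What to change.** 1. **SAP 7.4.1 and shells.** Present Tables 14.4.1.2 and 14.4.1.3 by SOC, PT and maximum severity (mild, moderate, severe) for each arm, counting each subject once per PT at the highest grade.
2. **SAP 6.9.4 and Protocol 10.5.6.4.** Reconcile the two sentences so that the classification behind Table 14.4.1.6 keeps the severity limb of its own definition. For example: a treatment-related event is a UADR when its type is off the list, or when its type is listed but its severity goes beyond the Brochure's description.

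**Cost.** Extra table columns, one sentence in each document, and possibly a few more UADR evaluations. No new data are needed. If a protocol amendment is not wanted, the first change needs the SAP only and closes the tabulation gap; the UADR ambiguity would then remain for site reporting under the Protocol.

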7. STATISTICAL METHODS

7.1. Primary Effectiveness Endpoint

The primary effectiveness endpoint will be duration of effect (regardless of responder status), defined as the number of days from Treatment Day (Baseline) to the day that GLS severity (Investigator assessment) at maximum frown returns to the Baseline value. Although the trial is not powered for inferential analysis, this will be the most influential outcome in the overall assessment of the effectiveness of prabotulinumtoxinA 40 Units, compared to prabotulinumtoxinA 20 Units, in treating moderate to severe glabellar lines. Analysis will be performed using the modified Intent-To-Treat (mITT) population and regardless of responder status.

Duration of effect will be described by Kaplan-Meier curves and the respective median times with associated 2-sided 95% confidence interval (CI) for each treatment group. Statistical analyses of treatment group differences will be done using Cox proportional hazards regression with time to return to Baseline as the dependent variable, treatment group as the independent variable, and age, gender, and Baseline GLS score (Investigator assessment) at maximum frown as covariates.

Statistical significance will be established at the 0.025 level with one-sided hypothesis testing.

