2.3. Primary Endpoint

The primary effectiveness endpoint will be duration of effect, defined as the number of days from Treatment Day (Baseline) to the day that GLS severity (Investigator assessment) at maximum frown returns to the Baseline value. The treatment will be considered to remain effective for the amount of time during which GLS severity at maximum frown has not returned to Baseline severity. Duration of effect will be estimated by Kaplan–Meier analysis.

Although the trial is not powered for inferential analysis, this will be the most influential outcome in the overall assessment of the effectiveness of prabotulinumtoxinA 40 Units, compared to prabotulinumtoxinA 20 Units, in treating moderate to severe glabellar lines.

Confidential Page 9/58

TABLE 1. SCHEDULE OF EVENTS AND PROCEDURES

Visit Number	V1 ¹ Screening	V2 ¹	V3	V4 (phone f/u)	V5 to V15 ²	V16 ³ (or Final Visit, or ET)	Unscheduled Visit 11
Day/Week/Month	≤ 14D	Tx Day	48Hr	D 7	D30 to D330 Monthly Visits	D365	
Visit Windows				±1 Day	D30 ±3D, ≥D60 ±7D	±14D	
Assessment and Procedures							
Informed Consent	X						
Inc/Excl Criteria	X						
Demographics, Med Hx	X						
Randomization to Study Tx 4		X					
Effectiveness - Investigator							
Glabellar Line Scale ⁵	X	X	X		X	X	X
Global Aesthetic Improvement			X		X	X	X
Effectiveness - Subject							
Glabellar Line Scale ⁵	X	X	X		X	X	X
7-Day Subject Diary		Х —		—			
Global Aesthetic Improvement			X		X	X	X
Subject Satisfaction Score			X		X	X	X
Clinical Interview 6					D30 only	X	X
Safety Evaluations							
Directed Questionnaire ⁷	X		X		X	X	X
Directed Review of Systems	X		X		X	X	X
Vital Signs 8	X		X		X	X	X
Physical Exam 9	X		X		X	X	X
UPT (as applicable)	X	X				X	
Clinical Laboratory Tests 10	X					X	X
ECG	X					X	X
Safety Assessment Phone Call				X			
Brow Area Photography	X	X	X		X	X	X
Concomitant Medications	X	X	X	X	X	X	X
AE Assessment		X	X	X	X	X	X

- 1. Screening and treatment visit can take place the same day, at the discretion of the investigator
- 2. Subjects will be followed monthly until their Glabellar Line Scale score is back to Baseline (Investigator assessment)
- 3. Subject exits study once their Glabellar Line Scale Score has returned to Baseline (Investigator assessment)
- 4. IP may be administered same day as Screening
- 5. Glabellar Line Scale at Maximum Frown, 0=none, 1=mild, 2=moderate, 3=severe
- 6. Clinical Interview Questions
 - What did you like about the treatment (clinically or other feedback)?

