7.5.1. Modified Intent-to-Treat Population

The mITT Population is defined as all subjects who were randomized, received their injection of IP, and have at least one post-dosing assessment for the primary effectiveness endpoint. The ITT principle will be followed in that subjects in the mITT population will be analyzed according to the treatment assigned as per the randomization schedule. The mITT Population will be the primary population used for effectiveness analyses of primary, secondary, tertiary, and exploratory effectiveness endpoints.

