7.7. General Considerations

Data will be listed by subject number. Data will be summarized by treatment and study visit, where applicable. For categorical parameters, the number and percentage of subjects/observations in each category will be presented; percentages will be based on the number of subjects in the relevant analysis population in each treatment group. For continuous parameters, descriptive statistics will include n (number of subjects or observations), mean, standard deviation, median, and range. A full description of the statistical methods planned for this study will be provided in the Statistical Analysis Plan (SAP). All programs for data output and analyses will be written in SAS version 9.4 or higher (SAS Institute, Inc., Cary, NC).

Missing Values: For the mITT analysis of primary, secondary, tertiary, and exploratory duration of effectiveness endpoints, in the case of a missed visit, subjects will be considered to have returned to Baseline if they are confirmed to have returned to Baseline at the next non-missed visit. Subjects will be considered to have to have returned to Baseline if they fail to attend 2 consecutive visits or drop out of the study. For missing observations for exploratory endpoints other than duration of effect data will be analyzed as observed without imputation.

Discontinuation and Drop-Outs: Dropouts will not be replaced. Subject disposition will summarize the number of subjects who were randomized and who discontinued from the study (including reasons for discontinuation).

Interim Analysis: An interim analysis will be conducted when >90% of subjects have completed Visit 8 (Day 120) to evaluate response to exposure (efficacy, duration) and adverse events. For assessment of the primary effectiveness endpoint, 95% CIs will be presented but statistical analyses will not be conducted and a statistical penalty for the final analysis will not be employed. While data by treatment group will be presented, individual subjects will not be unblinded.

Poolability of Investigative Sites: Data from all investigative sites will be pooled based on the assumption of clinical comparability: the same protocol will be used for all sites, all sites will be monitored for protocol compliance, and the same data collection instrument and methodology will be used across all sites.

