14.1 Subject Disposition

Table 14.1.1 Enrollment

Site	Screened	Screen Failures	Randomized	PP	ITT	SAFT
01	XX	XX	XX	XX	XX	XX
02	XX	XX	XX	XX	XX	xx
03	XX	XX	XX	XX	XX	XX
04	XX	XX	XX	XX	XX	xx
05	XX	XX	XX	XX	XX	XX
All sites	XX	XX	XX	XX	XX	XX

Number of subjects

Table 14.1.2 Subject Discontinuations with Primary Reason

Study Exit		PraB 40 (n = xx)	OnaB 20 (n = xx)	PraB 20 (n = xx)
Completion of Study	N	XX	XX	XX
	Completed up to return to BL	xx (xx.x%)	xx (xx.x%)	xx (xx.x%)
Primary Reason for d/c* prior	N	xx (xx.x%)	XX	XX
to return to BL	Adverse Event	xx (xx.x%)	xx (xx.x%)	xx (xx.x%)
	Lost to follow- up	xx (xx.x%)	xx (xx.x%)	xx(xx.x%)
	Withdrew consent	xx (xx.x%)	xx (xx.x%)	xx (xx.x%)
	Protocol violation	xx (xx.x%)	xx (xx.x%)	xx (xx.x%)
	Investigator Decision		xx (xx.x%)	xx (xx.x%)
	Other		xx (xx.x%)	xx (xx.x%)

Number of subjects (% in parenthesis). *d/c= discontinuation

Table 14.1.3 Listing of Subject Discontinuations

Subject	Treatment	Gender*	Age	Last Visit	Primary Reason for
Number	Group				Discontinuation
##-###	PraB 40	M/F	XX	V#	xxxxxxxxxxxxxxxx
##-###	PraB 20	M/F	XX	V#	xxxxxxxxxxxxxxx
##-###	OnaB 20	M/F	XX	V#	xxxxxxxxxxxxxxxx
##-###	OnaB 20	M/F	XX	V#	xxxxxxxxxxxxxxx
##-###	PraB 40	M/F	XX	V#	xxxxxxxxxxxxxxxx
##-###	PraB 20	M/F	XX	V#	xxxxxxxxxxxxxxx
##-###	PraB 40	M/F	XX	V#	XXXXXXXXXXXXXXXX
##-###	OnaB 20	M/F	XX	V#	XXXXXXXXXXXXXXXX

M=Male, F=Female

Version 1.1 31-May-2023 Confidential Page 24/58

Table 14.1.4 Subject Disposition per Visit

Disposition of Subjects at	PraB 40	OnaB 20	PraB 20
each Study Visit	(n = xx)	$(\mathbf{n} = \mathbf{x}\mathbf{x})$	$(\mathbf{n} = \mathbf{x}\mathbf{x})$
N	XX	XX	XX
V1 (screening)	xx (xx.x%)	xx(xx.x%)	xx(xx.x%)
V2 (pre-Tx)	xx(xx.x%)	xx(xx.x%)	xx (xx.x%)
V3 (48hr)	xx(xx.x%)	xx(xx.x%)	xx(xx.x%)
V4 (D7; phone f/u)	xx(xx.x%)	xx(xx.x%)	xx (xx.x%)
V5 (D30)	xx (xx.x%)	xx (xx.x%)	xx(xx.x%)
V6 (D60)	xx(xx.x%)	xx(xx.x%)	xx(xx.x%)
	xx(xx.x%)	xx(xx.x%)	xx (xx.x%)
	xx (xx.x%)	xx (xx.x%)	xx (xx.x%)
V16 (D365)	xx (xx.x%)	xx (xx.x%)	xx (xx.x%)

Number of subjects (% in parenthesis)

Table 14.1.5 Study Dates

FPFV	LPFV	LPLV	Enrollment Duration	Study Duration
dd-mmm-yyyy	dd-mmm-yyyy	dd-mmm-yyyy	XXX	XXX

FPFV= First Patient First Visit, LPFV= Last Patient First Visit, LPLV= Last Patient Last Visit. Enrollment duration=FPFV-LPFV+1, Study duration=FPFV-LPLV+1

Confidential Page 25/58

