14.3 Efficacy Response Data

14.3.1 Primary Effectiveness Endpoint - Duration of Effect

Table 14.3.1.1 Duration of Effect (Investigator; Regardless of Responder Status; PraB 40 vs PraB 20)

GLS (Investigator) Duration of Effect	PraB 40	PraB 20
(Return to Baseline GLS score)	$(\mathbf{n} = \mathbf{x}\mathbf{x})$	$(\mathbf{n} = \mathbf{x}\mathbf{x})$
Subject Status, n (%)		
Returned to BL (event)	xx (xx%)	xx (xx%)
Censored	xx (xx%)	xx (xx%)
Kaplan-Meier Estimates for Return to BL		
1 st Quartile, (95% CI)	x.x(x.x, x.x)	x.x(x.x, x.x)
Median, (95% CI)	x.x(x.x, x.x)	x.x(x.x, x.x)
3 rd Quartile, (95% CI)	x.x(x.x, x.x)	x.x(x.x, x.x)
Adjusted Hazard Ratio (95% CI)	x.xx (x.:	xx, x.xx)
Stratified Log-Rank p-value	p <x.< td="">xxxx	</x.<>	xxxx
Unadjusted Hazard Ratio (95% CI)	zard Ratio (95% CI) x.xx (x.xx, x.xx)	
Unstratified Log-Rank p-value	p <x.xxxx< td=""></x.xxxx<>	

Data for all subjects regardless of Responder status

Duration of effect in days, calculated from Visit 2 (Treatment Day) to when subject returns to Baseline GLS score Responder = At least 1-Point improvement in GLS (max frown)

Version 1.1 31-May-2023

Confidential Page 29/58

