GLS (Investigator) Duration of Effect (Return to Score 2 or higher)	PraB 40 (n = xx)	PraB 20 (n = xx)	PraB 40 (n = xx)	OnaB 20 (n = xx)	PraB 20 (n = xx)	OnaB 20 (n = xx)
Subject Status, n (%)						
Returned to BL (event)	xx (xx%)	xx (xx%)	xx (xx%)	xx (xx%)	xx (xx%)	xx (xx%)
Censored	xx (xx%)	xx (xx%)	xx (xx%)	xx (xx%)	xx (xx%)	xx (xx%)
Kaplan-Meier Estimates for Return to B	L					
1 st Quartile, (95% CI)	x.x(x.x, x.x)	x.x(x.x, x.x)	x.x(x.x, x.x)	x.x(x.x, x.x)	x.x(x.x, x.x)	x.x(x.x, x.x)
Median, (95% CI)	x.x(x.x, x.x)	x.x(x.x, x.x)	x.x(x.x, x.x)	x.x(x.x, x.x)	x.x(x.x, x.x)	x.x(x.x, x.x)
3 rd Quartile, (95% CI)	x.x(x.x, x.x)	x.x(x.x, x.x)	x.x(x.x, x.x)	x.x(x.x, x.x)	x.x(x.x, x.x)	x.x(x.x, x.x)
Adjusted Hazard Ratio (95% CI)	x.xx (x.xx,	, x.xx)	x.xx (x.xx, x.xx)		x.xx (x.xx, x.xx)	
Stratified Log-Rank p-value	p <x.xx< td="">xx	p<x.xx< td="">xx	p<x.xxxx< td=""></x.xxxx<>	</x.xx<>	</x.xx<>	xx	p <x.xx< td="">xx	p<x.xxxx< td=""></x.xxxx<>	</x.xx<>	xx	p <x.xxxx< td=""></x.xxxx<>	
Unadjusted Hazard Ratio (95% CI)	x.xx (x.xx,	, x.xx)	x.xx (x.xx, x.xx)		x.xx (x.xx, x.xx)	
Unstratified Log-Rank p-value	p <x.xx< td="">xx	p<x.xxxx< td="">p<x.xxxx< td=""></x.xxxx<>	</x.xxxx<>	</x.xx<>	xx	p <x.xxxx< td="">p<x.xxxx< td=""></x.xxxx<>	</x.xxxx<>		p <x.xxxx< td=""></x.xxxx<>	

Data for subjects deemed Responder at any point during the study

Time to Loss of Responder Status = Days from Treatment to first returning back to Score 2 or higher, after achieving Score 0 or 1

Version 1.1 31-May-2023

Confidential Page 40/58

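### Does the primary duration analysis need a written rule for subjects whose glabellar lines never improve?

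*SAP*

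**What the plan says.** SAP 7.1 runs duration from Treatment Day to "the day that GLS severity (Investigator assessment) at maximum frown returns to the Baseline value". It then states: "Analysis will be performed using the modified Intent-To-Treat (mITT) population and regardless of responder status". The footnotes to Table 14.3.1.1 repeat that all subjects are included and define a responder as at least 1 point better on the GLS, so non-responders are kept deliberately. SAP 7.5.1 asks only that mITT subjects were randomized, were injected and "have at least one post-dosing assessment for the primary effectiveness endpoint".

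SAP 2.3 regards treatment as continuing to "remain effective for the amount of time during which GLS severity at maximum frown has not returned to Baseline severity". The missing-value rules in SAP 7.7 cover a single missed visit, confirmed at the next attended one, and subjects counted as having "returned to Baseline if they fail to attend 2 consecutive visits or drop out of the study". Neither rule reaches a subject who attends every visit and stays at Baseline.

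Several places describe exit. SAP 2.1 and Protocol 4.1 end participation once the subject is at Baseline. Footnotes 2 and 3 of Table 1, in both documents, follow the subject until then. Protocol 10.2.5 permits exit for this reason on and after Day 90. The only completer row in Table 14.1.2 is "Completed up to return to BL".

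**The concern.** To return, a score must first have moved. For a subject whose Investigator GLS never leaves Baseline, three scorings can be argued.

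- **Censored late.** There was no return, so by the wording of SAP 2.3 the effect is still running. The subject is censored at the last visit, at the extreme Day 365.
- **Event at once.** Any post-dose score equal to Baseline counts, so the event falls at Visit 3 (48 hours) or Day 30. This would also turn a later responder whose effect has not yet begun into a Day 2 event.
- **Event at exit.** The subject is at Baseline when exit is allowed, so the event falls near Day 90.

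The SAP supplies the missing condition elsewhere. Table 14.3.3.1.6, an exploratory endpoint, counts days to "first returning back to Score 2 or higher, after achieving Score 0 or 1". The primary endpoint has no such clause. Late censoring would flatter whichever arm fails more often, and immediate events would mix speed of onset into duration. Either could move the medians and hazard ratio of what SAP 7.1 calls the most influential outcome.

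**Working it through.** **The plan's own figure.** Inputs from SAP 7.6: 50 per arm, 20U median 4 months, HR 0.47, 10% annual censoring, exponential times, one-sided 0.025. Follow-up is taken as 12 months. Monthly hazards are ln 2/4 = 0.1733 (20U) and 0.47 × 0.1733 = 0.0814 (40U). The censoring hazard is −ln(0.9)/12 = 0.0088.

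Expected events per arm = 50 × λ/(λ+c) × [1 − exp(−12(λ+c))], giving 42.2 and 29.8, about 72.1 in all. Schoenfeld power = Φ(½√72.1 × |ln 0.47| − 1.96) = Φ(1.245) = 89%. The stated 80% is not reproduced at 12 months; it appears with about 7 months of follow-up (80.2%). The plan is therefore conservative here.

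**How many never-improvers?** The documents do not say. The nearest figure is in Protocol 1.1: in the earlier Phase III trial with both toxins, 87.2% (95% CI 83.0 to 91.5) of the 20U prabotulinumtoxinA arm reached GLS 0 or 1 at Day 30. That leaves 12.8% (8.5 to 17.0) who did not. This is a ceiling, because a change from severe to moderate is an improvement that misses 0 or 1. Rates of 2%, 5% and 10% are assumed; in 50 subjects these are 1, 2.5 and 5.

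**Medians in closed form (p = never-improver share).** Censored late: 121.75 × ln[(1−p)/(0.5−p)]/ln 2. Event before the median: 121.75 × ln[(1−p)/0.5]/ln 2. For 20U:

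| p | Censored late | Early event |
|---|---|---|
| 2% | 125 days | 118 days |
| 5% | 131 days | 113 days |
| 10% | 142 days | 103 days |

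These are continuous-time values. The trial reads events at visits about 30 days apart, so an observed Kaplan-Meier median moves in visit-sized steps.

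**Power and rejection by simulation.** 50 per arm; return times read at Days 30 to 330 and 365; unadjusted Cox with Efron ties; one-sided 0.025. Monte Carlo error is up to about 1 point.

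| Never-improvers, 20U / 40U | Censored Day 365 | Censored Day 90 | Event Day 90 | Event Day 1 |
|---|---|---|---|---|
| 5% / 5%, HR 0.47 | 82% | 86% | 86% | 85% |
| 5% / 2%, HR 0.47 | 78% | 86% | 90% | 90% |
| 10% / 5%, HR 0.47 | 65% | 83-84% | 89% | 89% |
| 5% / 10%, equal durations (rejection) | about 7% | 3.2-3.9% | – | – |

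With no never-improvers, power is 88-89% under every scoring. At 2% in both arms it is 86% (censored Day 365) against 88% (event Day 90). In the 10%/5% case the estimated hazard ratio is 0.56 under Day 365 censoring, 0.48 under Day 90 censoring and 0.47 for an event at Day 90.

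Most of the loss in the first column comes from keeping the subject in the risk set for a year. Moving the same censoring to Day 90 recovers most of it.

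**Which scoring do the documents favour?** Late censoring needs a subject at Baseline severity to keep attending until Day 365 while counted as benefiting, against the exit provisions and the single completer row of Table 14.1.2. A Day 2 event strains the word for return. The figures for it (power 80%, 67%, 54%) rest on assumed slow-onset shares of 10%, 20% and 30% that have no source in the documents. An event at the exit visit fits the exit text and the disposition table together.

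**The case for a change.** The strongest case for a change is that an SAP exists to fix such choices before lock, and that this one prevails over the protocol. SAP 2.3, read literally, supports censoring. Exit at Day 90 is permitted, not required, and the provision governs exit and not the event date. The 48-hour question does not depend on never-improvers at all. SAP 1.3 limits the analyses to interpretation, yet SAP 7.1 still sets a one-sided 0.025 level, and the medians are what will be interpreted. At the 12.8% ceiling in 20U against 5% in 40U, power ranges from 55% (censored Day 365) to 92% (event at Day 0 or 2).

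What stands: the rule is unwritten, and one sentence would cost little. The exit wording also differs between SAP 2.1 with Protocol 4.1 and Protocol 10.2.5. Those passages must be reconciled, but that is a separate matter: for a subject who improved, the event date is the same under either.

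What does not stand is that the gap endangers the primary result. The wide spread pairs the ceiling rate with the least natural scoring.

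Nor is there one right rule to write in. Scoring never-improvers as events on Day 1 uses a day on which no GLS is taken. With equal responder durations it rejects in 3.6%, 4.6% and 6.6% of trials (never-improvers 5% v 2%, 10% v 5%, 10% v 2%), against 3.1-4.4% for an event at Day 90. If 40U fails more often (10% against 5%), its power falls to 72%. That is a choice of estimand and does not repair an error.

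**Conclusion.** No change is called for. This is missing detail that a competent analyst would fill sensibly: a subject at Baseline on leaving from about Day 90 is an event at that visit, and a 48-hour score before any improvement is not a return. On that reading power is 86-90% in the scenarios tabulated, above the 80% the plan states. Censoring at the same visit instead gives 83-86%.

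The SAP already shows the reader how much non-response matters. Tables 14.3.3.1.1 and 14.3.3.1.5 repeat the duration analysis in 1-point responders, where the question does not arise; a responder-only analysis simulates at 2.4-2.6% rejection and 86-88% power. Table 14.3.3.3.1 gives 1-point response rates by visit.

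The conclusion rests on never-improvers being a small group and on exit near Day 90. The Day 365 figures are a worst case under assumed rates. They would matter only if a sizeable share never improved and those subjects were nevertheless retained and censored for the full year.
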